1 SYNOPSIS

Title	⁶⁸GA-PSMA FUSION PET/MRI FOR IMAGE-GUIDED PROSTATE BIOPSIES
Principle Investigator	[name]
Study Center	Michigan Medicine
Primary Objective(s)	To determine the sensitivity and specificity of mpMRI alone, and mpMRI in combination with ⁶⁸ Ga-PSMA PET (i.e., fusion PET/MRI), for the detection of primary Gleason $\geq 3+4$ PCa. Our primary outcome will be to determine whether the positive likelihood ratio (LR) for ⁶⁸ Ga-PSMA PET-MRI is at least 1.28 greater than that of standard-of-care mpMRI.
Secondary Objective(s)	(1) Safety (2) Frequency of extraprostatic extension, lympho-nodal and/or other metastatic disease positive on ⁶⁸ Ga-PSMA and not identified by conventional imaging
Exploratory Objective	Exploratory assessment of radiomics texture analyses of mpMRI and ⁶⁸ Ga-PSMA PET identified lesions
Test drug(s)	
Name of active ingredient	⁶⁸ Ga-PSMA
Dose	3.0 – 7.0 mCi
Route of administration	Intravenous
Duration of treatment	Once
Indication	Prostate cancer
Diagnosis and main criteria for inclusion	Subjects must fulfill the following criteria: Males (≥ 18 years of age) with prior mpMRI resulting in at least one PI-RADS 3-5 lesion with clinical need for a prostate biopsy procedure can participate, if one of the 2 criteria apply: (1) Known Gleason 6 or 7 prostate cancer undergoing active surveillance or in the confirmation phase of active surveillance, or (2) Rising PSA with either a) no prior biopsy or b) single or multiple negative prior biopsies.
Exclusion criteria	Any criterion will result in ineligibility: (1) Prior prostate biopsy within 12 weeks prior to enrollment (2) Acute prostatitis within the last 6 months (3) Current non-urologic bacterial infection requiring active treatment with antibiotics (4) Active other malignancy (except basal cell or squamous cell skin cancer) within the last 2 years (5) Body weight greater than 350 lbs (158 Kg) (6) Inability or unwillingness to receive a prostate biopsy procedure (7) Unable to lie flat, still, or tolerate a PET/CT scan (8) Unable to provide own consent (9) Concurrent severe and/or uncontrolled and/or unstable medical disease other than prostate cancer (e.g. poorly controlled diabetes, congestive heart failure, myocardial infarction within 6 months prior to study participation, unstable and uncontrolled hypertension, acute renal failure of any intensity, chronic renal or hepatic disease, severe pulmonary disease) (10) Prisoner
Study phase	Phase 2
Study design	Open label, single-center, single-dose, diagnostic imaging efficacy study

Methodology	
Participating subjects already underwent a clinically indicated prostate MRI resulting in at least one PI-RADS 3-5 lesion performed within 3 months prior to recruitment.
 
Research imaging: ^{68}Ga-PSMA PET/CT.
 
Fusion of mpMRI and ^{68}Ga-PSMA PET and biopsy target selection from mpMRI and ^{68}Ga-PSMA PET.
 
Prostate biopsy procedure (clinically indicated): standard biopsy and additional targeted biopsies to obtain pathological proof. Biopsy targets are selected from mpMRI and ^{68}Ga-PSMA PET.

Type of control	Not applicable
Number of subjects	100
Safety Assessments	Patient vital signs will be taken before and after the administration of the radiopharmaceutical. The patients will also be asked to report adverse events.
Plan for statistical analysis	
Visual and semi-quantitative assessment of PET/CT images: Descriptive statistics, frequency tables.
 
We employ mixed effects logistic regression model to estimate the positive likelihood ratio (LR) of the combination of ^{68}Ga-PSMA-guided plus mpMRI-guided biopsy (fusion PET/MRI) for the detection of primary Gleason $\geq 3+4$ cancer is higher than for mpMRI-guided biopsy (using PI-RADS version 2) alone.

3 LIST OF ABBREVIATIONS AND DEFINITIONS OF TERMS

⁶⁸ Ga-PSMA	Gallium-68 labelled prostate-specific membrane antigen (PSMA-HBED-CC, or PSMA-11)
ADL	Activities of Daily Living
AE	Adverse event
ALARA	As low as reasonably achievable
AS	Active surveillance
BP	Blood pressure
BPH	Benign prostate hyperplasia
CRF	Case report form
CRPC	Castrate resistant prostate cancer
CT	Computed tomography
CTCAE	Common Terminology Criteria for Adverse Events
DICOM	Digital imaging and communications in medicine
FWHM	Full width at half maximum
GC	Gas chromatography
GCP	Good clinical practice
HPLC	High-performance liquid chromatography
i.v.	Intravenous
IHC	Immunohistochemistry
INR	International normalized ratio
IRB	Internal review board
LC	liquid chromatography
MRI	Magnetic resonance imaging
mpMRI	Multi-parameter MRI
OSEM	ordered-subset expectation maximization
p.i.	post injection
PCa	Prostate cancer
PET	Positron emission tomography
PET/CT	Hybrid PET with CT
PET/MRI	Positron emission tomography with magnetic resonance imaging
PI	Principal investigator
PI-RADS	Prostate Imaging Reporting and Data System
pPCa	Primary prostate cancer
PSA	Prostate-specific antigen
ROC	Receiver operating characteristic
SAE	Serious adverse event
SD	Standard deviation
SID	Stable isotope dilution
SUV	Standardized uptake value
SOG	Study operation guide
TBR	Tumor-to-background ratio
TRUS	Transrectal ultrasound
VOI	Volume of interest

List of Definitions

Mass dose	Amount of ^{68}Ga - labeled drug substance (“hot” fraction of the active compound, ^{68}Ga -PSMA), plus non-radioactive drug substance, expressed in μg
Radioactive dose	Amount of active ^{68}Ga - labeled drug substance (“hot” fraction of the active compound, ^{68}Ga -PSMA), expressed in MBq
Impurities	Everything not considered in the Mass dose, e.g. by-products, degradation products, radiolysis products
Total quantity	Mass dose plus impurities (for a study following the microdosing concept the total quantity must remain $\leq 100 \mu\text{g/human}$)

4 BACKGROUND INFORMATION

4.1 Introduction

Primary prostate cancer (PCa) represents a broad spectrum of disease, ranging from indolent to aggressive and death-causing illness. The highly heterogeneous nature of PCa provides a significant challenge for clinical disease management.^{1,2} Organ-confined PCa is an overdiagnosed and overtreated disease, which may result in life-changing side effects.³ This overtreatment is in part related to the inability to accurately identify PCa with elevated risk. Standard of care management of rising prostate-specific antigen (PSA) levels followed by standard systematic (non-targeted) prostate biopsies is unsatisfactory and leads to the detection of low grade prostate cancer at high rate while - at the same time - missing many significant (Gleason score $\geq 3+4$) cancers.⁴ The positive predictive value of the standard prostate biopsy is only approximately 30% at a PSA level $> 4.0 \text{ ng/mL}$.⁵ Accordingly, the recommendation by the United States Preventive Services Taskforce (USPSTF) against PSA screening in 2012 has led to a reduction of the number of PSA tests and prostate biopsies being performed.⁶ While this will likely reduce the costs associated with low-risk PCa, it may inadvertently cause a reverse stage migration to more men presenting with advanced disease. It was estimated that omitting PSA screening may lead to a doubling of metastatic disease rates as early as 2025, which would generate many avoidable cancer deaths.⁷

Clearly, a highly accurate, ideally non-invasive, precision imaging test to differentiate low-risk disease from intermediate/high-risk PCa is needed. Accurate imaging allows subsequent tissue verification (via targeted biopsy) of suspicious lesions. Multiparametric magnetic resonance imaging (mpMRI) at 3 Tesla — due to its ability to detect clinically significant PCa and minimize detection of clinically insignificant disease — has been advocated for this task.⁸ In fact, mpMRI applying the Prostate Imaging Reporting and Data System (PI-RADS version 2) scoring criteria⁹ have demonstrated rising detection rates of significant PCa with increasing PI-RADS scores when combined with targeted prostate biopsies. Image-guided (targeted) prostate biopsies based on mpMRI clearly outperform non-targeted biopsies.^{10,11} However, the performance of this approach remains suboptimal for the task of identification of significant disease with high precision.^{12,13} In the recent multicenter paired-cohort PROMIS trial of 740 men, the sensitivity of mpMRI for clinically significant prostate cancer was 93%, but the specificity was only 41%, indicating a high false positive rate.¹¹ When mpMRI is compared to whole-gland pathology from prostatectomy specimens, results are less encouraging. Combining 2 recent studies with a total of 275 subjects (performed at highly experienced institutions), the sensitivity for identification of any Gleason ≥ 7 PCa was below 80%, while at the same time a significant number of low-risk cancers were falsely “overstaged” (specificity 54 – 68 %).^{12,14} Furthermore, interpretation of mpMRI, even when using standardized reporting methods (PI-RADS), is difficult and requires considerable training. Among highly experienced prostate MRI specialists, inter-observer variability using PI-RADS classifiers remains too high ($\kappa = \sim 0.5-0.6$).¹⁵

Optimizing the performance of mpMRI—in particular, improving the specificity—is important. We recently published an interim analysis on 36 subjects with 52 mpMRI-identified lesions (Likert scale: low, intermediate, high risk) that showed the addition of ¹⁸F-choline PET/CT to mpMRI significantly improves the identification of Gleason $\geq 3+4$ PCa over mpMRI alone.¹⁶ Pathology was obtained from mpMRI-guided plus 12-sample standard biopsies. Our unpublished final results obtained from 56 subjects with 90 mpMRI-identified lesions (40 low, 30 intermediate, 20 high risk) indicate that ¹⁸F-choline significantly improved the differentiation between clinically significant PCa (Gleason $\geq 3+4$) and low-risk or benign disease in men assigned an intermediate-risk score by mpMRI. Furthermore, we were able to demonstrate that the combination of ¹⁸F-

choline PET with mpMRI was cost-effective (respective manuscripts have been submitted for publication in “Radiology”).

While these results demonstrate that precision imaging utilizing a combination of molecular (PET) data with mpMRI is can be superior to mpMRI alone, the chosen radiotracer (¹⁸F-choline, as ¹⁸F-choline PET/CT) is ultimately not sufficient for the diagnosis of primary PCa because elevated choline uptake is commonly seen in benign prostatic hyperplasia (BPH) nodules.¹⁷ Under these circumstances, future approval for ¹⁸F-choline by the U.S. Food and Drug Administration (FDA) for initial staging of PCa is highly unlikely and alternative strategies are needed.

4.1.1 Significance of PSMA and preliminary data for PET imaging with ⁶⁸Ga-PSMA

In recent years, ⁶⁸Ga-labeled ligands to PSMA have shown great promise for PET imaging of recurrent PCa. Particularly important is the fact that radiolabeled small molecules binding to PSMA are capable of identifying PCa at very low PSA levels, opening the door for early targeted treatment of disease recurrence.¹⁸⁻²² There is also substantial evidence that ⁶⁸Ga-PSMA outperforms ¹¹C/¹⁸F-choline for this indication.²³⁻²⁶ In contrast to ¹¹¹In-capromab-pendetide (ProstaScint), these ligands bind to the extracellular domain of this transmembrane glycoprotein and are internalized due to the enzymatic activity of PSMA, which leads to trapping of diagnostic (and therapeutic) radionuclides based on PSMA expression.

PSMA is expressed physiologically in the prostate at low levels as a cell surface protein, and is overexpressed in PCa, particularly in metastatic castration-resistant PCa. In fact, there is growing evidence that PSMA expression increases as a function of tumor aggressiveness and Gleason scores,^{27,28} which is a highly useful feature for the differentiation of significant from indolent primary PCa. Accordingly, ⁶⁸Ga-PSMA provides excellent target-to-background contrast suitable for PET/CT imaging of PCa.^{18,29}

While data are still limited, several retrospective reports indicate utility of ⁶⁸Ga-PSMA PET/CT to diagnose and localize primary PCa.^{19,26,30,31} In a small series with 20 patients receiving ¹¹C-choline and ⁶⁸Ga-PSMA PET/CT, both tracers identified all biopsy-proven significant primary PCa, but ⁶⁸Ga-PSMA lesion uptake was significantly higher than that of ¹¹C-choline, facilitating lesion detection.²⁶ Most importantly, ⁶⁸Ga-PSMA standardized uptake values (SUV) increase with Gleason grading, an important prerequisite for the identification of significant disease. In fact, a drastic increase in ⁶⁸Ga-PSMA uptake is found for Gleason $\geq 3+4$ PCa relative to low-grade disease and benign prostate, with little overlap between groups.³² In addition, ⁶⁸Ga-PSMA also appears to have utility for lymph node staging.³³ Based on our pilot data (**Figure 1**) and as demonstrated by Eiber et al.,¹⁹ hybrid or fusion ⁶⁸Ga-PSMA PET/MRI seems to be particularly useful for the localization and staging of primary disease within the prostate gland with a precision necessary for successful image-guided targeting at biopsy. The current literature regarding this topic is summarized in Bailey et al.³⁴

The immunohistochemical (IHC) expression of PSMA has been linked to aggressive features in localized (primary) PCa. PSMA overexpression has been associated with a higher rate of local recurrence after prostatectomy,³⁵ further substantiating a potential link of ⁶⁸Ga-PSMA uptake and aggressiveness. This is an important requisite of ⁶⁸Ga-PSMA when considering patient management within an active surveillance population, particularly since PSA and PSA kinetics are insufficient predictors of aggressive disease.³⁶ In addition, PSMA is also a promising target for PCa-specific radionuclide therapies.³⁷

⁶⁸Ga-PSMA is not completely specific for PCa, as IHC PSMA expression has been found in the neo-

vasculature of regenerative and reparative conditions.^{38,39} Also, recent case reports indicate elevated ⁶⁸Ga-PSMA uptake in pulmonary infections (tuberculosis), non-prostatic malignancies (lung cancer, lymphoma),^{40,41} benign neoplasms,⁴² and trauma. Nonetheless, in Figure 1, we demonstrate the utility of ⁶⁸Ga-PSMA for the distinction of cancer and inflammation in the prostate. While both mpMRI scans in the figure were reported prospectively as high risk for aggressive PCa (PI-RADS 5), elevated ⁶⁸Ga-PSMA uptake was seen only in PCa, but not in the site(s) of granulomatous inflammation.

Though the vast majority of aggressive prostate cancers express PSMA and display increasing IHC staining intensities with increasing Gleason scores,²⁸ a small subset of aggressive PCa appears to lack PSMA expression. Accordingly, the potential for absent ⁶⁸Ga-PSMA uptake in aggressive primary PCa needs to be considered.

4.1.2 Radiomics

Traditionally, medical images are treated as pictures intended solely for visual interpretation, which undercuts their information rich nature as mineable data.⁴³ Most human cancers exhibit strong molecular, morphological and phenotypic differences that are not easily assessable with standard image analysis techniques.⁴⁴ Comprehensive quantification of imaging features, called radiomics, can extract such image metrics (intensity, shape, texture, etc.) into mathematical classifiers of the tumor diagnostic or prognostic phenotype from single or hybrid anatomical and functional images.⁴⁵⁻⁵⁰ An example is shown in **Figure 1**. This is particularly useful in case of PCa, which often presents as heterogeneous multifocal disease of varying clinical significance.⁵¹ Fehr *et al.* showed that texture features from mpMRI could achieve good classification of Gleason patterns.⁵² Radiomics not only serves classification purposes, but can also aid in understanding the underlying biology of the observed imaging phenotype and the risk variations among the different foci of the disease, subsequently informing clinical staging and effective image-guided therapeutic intervention in PCa.⁵³

Since the utility of radiomics analyses are unknown for the combination of ⁶⁸Ga-PSMA and mpMRI, we will retrospectively assess its value to identify significant primary PCa.

[figure not shown]

Figure 1. Registered axial ⁶⁸Ga-PSMA PET (A,G; SUV range 0 – 10 for both scans), T2W MRI (B,H), ADC map (C,I), PET/MRI (D,J), and radiomics texture map from PET (E,K) and ADC (F,L) of two subjects for which a mpMRI resulted in a PI-RADS 5 lesion. **Upper panel (A-F), case 1:** Right apical Gleason 4+3 PCa (orange arrows), identified at targeted biopsy with intense focal ⁶⁸Ga-PSMA uptake (SUV median 7.0). The ⁶⁸Ga-PSMA texture map (E) shows a high degree of heterogeneity within the tumor. **Lower panel (G-L), case 2:** targeted biopsy resulted in active granulomatous inflammation (blue arrows) without elevated ⁶⁸Ga-PSMA uptake (SUV median 1.4). Texture map from ⁶⁸Ga-PSMA PET showed low heterogeneity, while texture maps from ADC are very similar for both cases (F, L).

5 STUDY OBJECTIVES AND PURPOSE

The primary study aim is the prospective comparison of standard-of-care mpMRI vs. combined ⁶⁸Ga-PSMA PET and mpMRI (⁶⁸Ga-PSMA fusion PET/MRI) for the detection and risk-stratification of clinically significant primary PCa.

Following (clinical) mpMRI and (research) ⁶⁸Ga-PSMA PET/CT imaging, we will perform targeted and standard 12-sample prostate biopsies. Biopsy targets will be defined from mpMRI and ⁶⁸Ga-PSMA PET; mpMRI interpretation will be done in accordance with PI-RADS v2.

Primary objective: We will determine the sensitivity and specificity of mpMRI alone and mpMRI in combination with ⁶⁸Ga-PSMA PET (i.e., fusion PET/MRI) for the detection of primary Gleason $\geq 3+4$ PCa. Primary outcome measure: determination whether the positive likelihood ratio (LR) for ⁶⁸Ga-PSMA PET-MRI is at least 1.28 greater than that of standard-of-care mpMRI. Reference standard will be pathology defined as targeted plus standard prostate biopsy, and prostatectomy, when available.

Secondary objective: We will determine the safety of ⁶⁸Ga-PSMA. We will also determine frequency and location of ⁶⁸Ga-PSMA positive lesions, such as potential extra-prostatic extension, lympho-nodal and/or distant metastatic disease positive on ⁶⁸Ga-PSMA but not identified by conventional (standard) imaging. While histological verification would be desirable, the decision for or against tissue verification will depend on clinical decisions making only, and not be required due to study participation.

Exploratory objective: We will evaluate whether radiomics classifiers (obtained from mpMRI and ⁶⁸Ga-PSMA identified targets) could improve identification and risk stratification of significant PCa. Reference standard will be pathology defined as targeted plus standard prostate biopsy, and prostatectomy, when available.

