12.1 Sample size determination

Sample size calculation was made for the primary objective only. We assess potential differences between the predictive performances of the two models (1) and (2), while maintaining ethical and economic considerations. We consider the positive likelihood ratio (positive LR) as a performance measure, which is defined by a ratio of sensitivity to 1-specificity. A higher positive LR means greater predictive information of positive test results irrespective of disease prevalence. Based on preliminary data obtained from mpMRI, we assume that the sensitivity and specificity of model (1) are both given by 0.789. For model (2), we assume conservatively that the sensitivity will be increased by 0.02 (2%) and that the specificity would improve by 0.15 (15%). In this scenario, the positive LR of model (1) is given by 3.74 and the positive LR of model (2) is calculated as 5.02. In order to detect the 1.28 difference in positive LR between the two models, we need at least 100 subjects, including at least 38 of 100 subjects with a histological diagnosis of significant PCa. The sample size was estimated as described in the literature.⁵⁸

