12.2 Significance Level

All statistical tests will use a 0.05 significance level.

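### The primary outcome uses the planning difference of 1.28 in positive LR as its bar; at the printed LR of 5.02 that bar is reached about half the time, and the written gains do not give 5.02

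*Combined protocol and SAP*

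**What the plan says.** The synopsis and section 5 define the primary outcome in the same way; in section 5 it is the "determination whether the positive likelihood ratio (LR) for ⁶⁸Ga-PSMA PET-MRI is at least 1.28 greater than that of standard-of-care mpMRI".

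Section 12.1 shows where the number comes from. For mpMRI, "we assume that the sensitivity and specificity of model (1) are both given by 0.789". Adding PET is assumed to raise sensitivity by 0.02 and specificity by 0.15. It then states that "the positive LR of model (1) is given by 3.74 and the positive LR of model (2) is calculated as 5.02", and continues: "In order to detect the 1.28 difference in positive LR between the two models, we need at least 100 subjects", of whom at least 38 should have significant cancer. Power and sidedness are not given, and the method is given only by citation.

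The primary-objective paragraph of section 12 (before 12.1) tests whether the PET coefficient in a mixed-effects logistic model differs from zero, and compares the two models' positive LRs by looking at their confidence intervals. Section 12.2 adds: "All statistical tests will use a 0.05 significance level". No section says whether 1.28 is to be met by the estimate or by a confidence limit.

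**The concern.** Detecting a difference of 1.28 means rejecting no difference when the truth is 1.28. Showing that the LR is greater by 1.28 or more is a different and harder claim. One number serves as both the effect assumed true and the bar to be cleared. When truth and bar coincide, the estimate falls short in about half of trials, and enrolling more men does not change that. A rule on the point estimate also has a false-positive rate that the 0.05 in section 12.2 does not control. What is at stake is the meaning of the primary result: a tracer that performed at the printed LR could be reported as having missed its primary outcome.

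**Working it through.** **Inputs.** From 12.1: sensitivity and specificity 0.789 for model (1), gains 0.02 and 0.15, printed LRs 3.74 and 5.02, and 100 subjects with at least 38 cancers (38/62). Table 1 expects 48 cancers, so 48/52 was also run. The documents give no figure for the dependence between the two reads of the same man, so it is assumed and varied: joint positive probability = (1 − w)·p1·p2 + w·min(p1, p2), from w = 0 (independent) to w = 1 (nested, or identical when the rates are equal).

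**Step 1, the plan's own figures.** Positive LR = sensitivity / (1 − specificity).

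- Model (1): 0.789/0.211 = 3.74. This reproduces.
- Model (2) with the written gains: 0.809/(1 − 0.939) = 0.809/0.061 = 13.26. The difference is 9.52, not 1.28.
- The printed 5.02 is 0.809/0.161, that is, specificity 0.839 and a gain of 0.05. Unrounded, the difference is 1.2855.

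**Step 2, chance of clearing 1.28** (simulated paired reads, 100,000–200,000 trials per setting; the larger-N and confidence-limit runs used within-subject correlations of 0 and 0.4).

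| True LR, model (2) | Observed difference ≥ 1.28, N = 100 | Same, larger N | Lower 95% Wald limit of the difference ≥ 1.28 |
|---|---|---|---|
| 5.02 | 47–50% | 50% at 400; 50–51% at 2,000; 52% at 20,000 | about 0% at 100; about 2.5% at 20,000 |
| 13.26 | 97–100% | about 100% from 400 | about 0% at 100; about 100% at 2,000 |

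The drift to 52% arises only because the unrounded 1.2855 lies slightly above 1.28.

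**Step 3, equal LRs** (3.74 for both, 38/62). The observed difference reaches 1.28 in 19% of trials at w = 0, 12% at 0.5, 5% at 0.8, 0.8% at 0.95 and 0% at w = 1.

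**Step 4, power against no difference at N = 100** (38/62, two-sided 0.05, log LR scale). For independent reads, the variance of each log LR is (1 − sens)/(sens·38) + spec/((1 − spec)·62).

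- 5.02 against 3.74: variances 0.0674 and 0.0903, SE of the difference √0.1576 = 0.397, effect ln(5.02/3.74) = 0.295, z = 0.744. Power = Φ(0.744 − 1.96) = 11%. For 80% power, N = 100·(2.80/0.744)² ≈ 1,417.
- 13.26 against 3.74: variances 0.0674 and 0.2545, SE √0.3218 = 0.567, effect 1.266, z = 2.23. Power = Φ(0.27) = 61%. For 80% power, N ≈ 158.

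Pairing helps. Simulated power of a paired log-LR test at 5.02 is 10%, 15%, 24% and 42% for w = 0, 0.5, 0.8 and 1. Under the 0.15 gain it is about 65–98% over the same range, counting trials with no model (2) false positive as successes.

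**The case against.** The strongest reply is that no pass/fail rule on 1.28 is written down. Section 5 speaks of determining whether; the formal test in section 12 is against zero, and the argument about sample size does not touch that test. This stands in part, which is why both the estimate and the confidence-limit readings are shown. But a non-zero PET coefficient does not show that the LR is greater by 1.28, and that is the stated primary outcome.

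A minimum worthwhile gain is also a legitimate choice in a phase 2 imaging study. That stands as a principle. The documents give no reason for 1.28 as such a margin, and a real margin requires sizing for a true effect above it.

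Three stronger readings go too far.

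- A reader might infer that the trial has an even chance of missing its outcome if PET/MRI performs as assumed. That holds only for the printed 5.02. The written gains give 13.26, and the bar is then almost always cleared on the estimate.
- A reader might set a 19% false-positive rate against the stated 0.05. The 19% needs independent reads, which is implausible when model (2) contains the same mpMRI read, and section 12.2 concerns tests, not a comparison of estimates.
- A reader might conclude that rewording is enough. Step 4 shows that it is not.

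Separately, section 12 defines model (1) as PI-RADS ≥ 3, while 0.789/0.789 is its figure for PI-RADS ≥ 4. That mismatch needs its own correction; the figures here follow 12.1.

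**Conclusion.** The point holds in conditional form. The stated primary outcome borrows a planning effect as its bar, and neither available reading of the plan makes 1.28 a sound criterion. If 5.02 is meant, success on the estimate is about 50% at any practical N and on a lower 95% limit at most about 2.5%. If the 0.15 specificity gain is meant, 1.28 does not follow from the inputs; replacing it by 9.52 would again set the bar at the assumed effect. A point-estimate rule is also uncontrolled at 0.05: with equal LRs it is met in 0–19% of trials at 38/62, depending on dependence between reads.

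These figures rest on the sensitivities and specificities in 12.1, one paired reading per subject, and an assumed range of dependence. They do not establish which of 5.02 and 0.15 the sponsor intended, nor that a formal pass/fail rule was adopted.

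**What to change.** In the synopsis and section 5, state the primary outcome as whether the positive LR of fusion PET/MRI exceeds that of mpMRI, by a paired comparison (ratio above 1, or difference above 0) at two-sided 0.05. Keep the planning effect in 12.1 only, correct it so that the LR, the difference and the 0.15 gain agree, and report the estimated difference with its interval beside it. If a superiority margin is truly wanted, justify it clinically and size for a larger true effect.

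The text change is small, but it has two costs. Success would then mean better than mpMRI, not better by a named amount; the interval still shows the amount. And the power in step 4 has to be faced: 12.1 must state the power, sidedness and read dependence assumed, and the power that 100 subjects deliver. If 5.02 is the intended alternative, the sample size itself has to be reconsidered.
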